4.4. Lifestyle Requirements

In order to participate in the study, subjects must be made aware of the following lifestyle guidelines and restrictions that apply during the study period. Details of these life style guidelines are provided in the sections as noted.

- On designated study visit days, comply with fasting requirements for at least 9 hours prior to visit (See [Section 6](#)). On study visit days, subject should not take the in-clinic dose of study medication before the clinic visit.
- On study visit days, do not smoke or ingest caffeine (eg, tea, coffee, some soft drinks/colas/energy drinks and power bars) during the 30 minutes prior to blood pressure and pulse (heart) rate measurements.
- On study visit days, take prescribed permitted concomitant medication, as needed, prior to the study visit, if it can be administered with water only.
- Avoid vaccinations with live or attenuated live vaccines and contact with individuals who have recently received live or attenuated live vaccines (See [Section 4.4.4](#)).
- Discontinue and avoid using certain medications and treatments (see [Inclusion Criteria](#) and list of prohibited medications in [Section 5.8.4](#) and [Appendix 4](#)).
- Contact the study site investigator if there are any changes or additions to concomitant medications.
- Avoid having elective surgery (See [Section 4.4.5](#)).
- Agree to use highly effective contraceptive methods per [Section 4.4.6](#).

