5.8.3. Rescue Therapy

The only medications that are allowed for rescue are listed in [Appendix 6](#).

Increases of acetaminophen/paracetamol and opioids are allowable as rescue medication for no more than 10 consecutive days. Acetaminophen/paracetamol may be added or increased to a maximum of 2.6 gm/day. Combination products such as over-the-counter “cold remedies” or pain medications should be assessed for acetaminophen/paracetamol content so as the total dose will not exceed 2.6 gm/day. Opioids may be added or increased to a maximum potency equivalent of 30 mg of orally-administered morphine.

Subjects who require rescue for more than 10 consecutive days will be discontinued from the investigational product and be designated as discontinued from the investigational product for lack of efficacy. There is no limit to the duration of nonconsecutive use of rescue medications. In addition, subjects may not be dosed with rescue medication during the 24 hours prior to a study visit. In the judgement of the investigator, if rescue therapy has any effect on efficacy data collected during a study visit, this will constitute a protocol deviation. Baseline stable use of acetaminophen/paracetamol or opioids should NOT be discontinued in advance of study visits.

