- Laboratory testing: Urine Pregnancy Test (for women of childbearing potential only), hsCRP;

- [REDACTED]

- [REDACTED]

The following procedures can be done before or after dosing depending upon the clinic's schedule but it is recommended that they be done at the same time (before or after dosing) consistently across all subsequent subject clinic visits:

- Targeted physical examination (examination of heart, lungs, abdomen, lower extremities, skin (presence of rash) and lymph nodes);
- Weight (without shoes preferred);
- Specific Medical History: History of uveitis, psoriasis, inflammatory bowel disease and peripheral articular involvement as assessed by swollen joint count;
- BASMI (linear function) by qualified blinded assessor: Lateral spinal flexion, tragus-to-wall distance, lumbar flexion (modified Schober), maximal intermalleolar distance and cervical rotation;
- Spinal mobility obtained by qualified blinded assessor: chest expansion;
- Assessment of swollen joints (44-joint count) by qualified blinded assessor;
- Assessment of enthesitis using the MASES Index by qualified blinded assessor;
- Complete drug accountability.

After dosing:

- 
- Monitoring of adverse events and concomitant medications. Record any modifications, deletions or additions;
- Contraception check: Confirm and document that proper contraception is being used;
- Contact IWRS and dispense new supply of investigational product to subject;
- Instruct subject not to take the in-clinic dose of investigational product the day of the next study visit and to bring the drug supply with them to the visit.

6.2.5. Week 12

There is a ± 7 day window for this visit.

- All PROs should be completed prior to any other study procedures. These include the following: ASAS/ASDASCRP Component: "Patient Global Assessment of Disease (NRS)", "Patient Assessment of Spinal Pain" which includes Total Back Pain (NRS) and Nocturnal Spinal Pain (NRS), BASDAI (NRS), BASFI (NRS), and FACIT-F.

After the PROs are obtained, the following procedures should be completed prior to dosing:

- Verify morning dose of investigational product was not administered by subject. If the dose was administered, continue with visit but re-instruct subject on the requirement for in-clinic dosing;

Note: For subjects where the visit is conducted in the afternoon or evening, verify the afternoon or evening dose of investigational product was not administered by the subject.

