- Vital signs: Blood pressure (seated), pulse rate and temperature (via tympanic, oral or temporal, preferred);
- Laboratory testing: Hematology, Chemistry Panel, Urinalysis, Urine Pregnancy Test (for women of childbearing potential only), hsCRP;
- Administer in-clinic dose of investigational product from previously dispensed study drug supplies.

The following procedures can be done before or after dosing depending upon the clinic's schedule but it is recommended that they be done at the same time (before or after dosing) consistently across all subsequent subject clinic visits:

- Targeted physical examination (examination of heart, lungs, abdomen, lower extremities, skin (presence of rash) and lymph nodes);
- Weight (without shoes preferred);
- BASMI (linear function) by qualified blinded assessor: Lateral spinal flexion, tragus-to-wall distance, lumbar flexion (modified Schober), maximal intermalleolar distance and cervical rotation;
- Spinal mobility obtained by qualified blinded assessor: chest expansion;
- Assessment of swollen joints (44-joint count) by qualified blinded assessor;
- Assessment of enthesitis using the MASES Index by qualified blinded assessor;
- Complete drug accountability.

After dosing:

- Monitoring of adverse events and concomitant treatments. Record any modifications, deletions or additions;
- Contraception check: Confirm and document that proper contraception is being used;

- Contact IWRS and dispense new supply of investigational product to subject;
- Instruct subject not to take the in-clinic dose of investigational product the day of the next study visit but to bring the drug supply with them to the visit.

6.2.6. Week 16

There is a ± 7 day window for this visit.

Subjects are required to fast for at least 9 hours prior to the visit; however, blood collection for laboratory testing may be taken up to 48 hours prior to or following this visit as necessary to ensure the samples are collected in a fasting state. If the blood collection is completed in advance of the clinic visit, the PROs should not be done with the blood collection but at the clinic visit.

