- All PROs should be performed before any other study procedures at the clinic visit. These include the following: ASAS/ASDAS_{CRP} Component: “Patient Global Assessment of Disease (NRS)”, “Patient Assessment of Spinal Pain” which includes Total Back Pain (NRS) and Nocturnal Spinal Pain (NRS), BASDAI (NRS), BASFI (NRS), ASQoL, SF-36v2, EQ-5D-3L and EQ-VAS, FACIT-F, - WPAI and AS-HCRU Questionnaire.
- Verify morning dose of investigational product was not administered by subject. If the dose was administered, continue with visit but re-instruct subject on the requirement for in-clinic dosing;

Note: For subjects where the visit is conducted in the afternoon or evening, verify the afternoon or evening dose of investigational product was not administered by the subject.

- Blood pressure (seated), pulse rate and temperature (via tympanic, oral or temporal, preferred);
- 12-lead electrocardiogram submitted to central reader;
- Laboratory testing: Central laboratory tests include: Hematology, Urinalysis, Chemistry Panel, Lipid Profile (fasting), Urine Pregnancy Test (for women of childbearing potential only), hsCRP;
- Blood sample for FACS Analysis;
- Complete Physical Examination: General appearance, skin (presence of rash), HEENT (head, eyes, ears, nose and throat), lungs (auscultation), heart (auscultation for presence of murmurs, gallops, rubs), lower extremities (presence of peripheral edema), abdominal (palpation and auscultation), neurologic (mental status, station, gait, reflexes, motor and sensory function, coordination) and lymph nodes;

- Weight (without shoes preferred);
- Specific Medical History: History of uveitis, psoriasis, inflammatory bowel disease and peripheral articular involvement as assessed by swollen joint count;
- BASMI (linear function) by qualified blinded assessor: Lateral spinal flexion, tragus-to-wall distance, lumbar flexion (modified Schober), maximal intermalleolar distance and cervical rotation;
- Spinal mobility obtained by qualified blinded assessor: chest expansion;
- Assessment of swollen joints (44-joint count) by qualified blinded assessor;
- Assessment of enthesitis using the MASES Index by qualified blinded assessor; Complete drug accountability;
- Monitoring of adverse events and concomitant treatments. Record any modifications, deletions or additions;
- Contraception check: Confirm and document that proper contraception is being used;

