Subjects will be switched to open-label tofacitinib 5 mg BID for the remainder of the study.

- Contact IWRS and dispense new supply of open-label investigational product to subject;
- Administer in-clinic dose of investigational product from open-label study drug supply.
- Instruct subject not to take the in-clinic dose of investigational product the day of the next study visit but to bring the drug supply with them to the visit.

6.2.7. Week 24

There is a ± 7 day window for this visit.

- All PROs should be completed prior to any other study procedures. These include the following: ASAS/ASDAS_{CRP} Component: “Patient Global Assessment of Disease (NRS)”, “Patient Assessment of Spinal Pain” which includes Total Back Pain (NRS) and Nocturnal Spinal Pain (NRS), BASDAI (NRS), BASFI (NRS), and FACIT-F.

After the PROs are obtained, the following procedures should be completed prior to dosing:

- Verify morning dose of investigational product was not administered by subject. If the dose was administered, continue with visit but re-instruct subject on the requirement for in-clinic dosing;

- Note: For subjects where the visit is conducted in the afternoon or evening, verify the afternoon or evening dose of investigational product was not administered by the subject. Vital signs: Blood pressure (seated), pulse rate and temperature (via tympanic, oral or temporal, preferred);
- Laboratory testing: Hematology, Chemistry Panel, Urinalysis, Urine Pregnancy Test (for women of childbearing potential only), hsCRP;
- Administer in-clinic dose of investigational product from previously dispensed study drug supplies.

The following procedures can be done before or after dosing depending upon the clinic's schedule but it is recommended that they be done at the same time (before or after dosing) consistently across all subsequent subject clinic visits:

- Targeted physical examination (examination of heart, lungs, abdomen, lower extremities, skin (presence of rash) and lymph nodes);
- Weight (without shoes preferred);
- BASMI (linear function) by qualified blinded assessor: Lateral spinal flexion, tragus-to-wall distance, lumbar flexion (modified Schober), maximal intermalleolar distance and cervical rotation;
- Spinal mobility obtained by qualified blinded assessor: chest expansion;
- Assessment of swollen joints (44-joint count) by qualified blinded assessor;
- Assessment of enthesitis using the MASES Index by qualified blinded assessor;
- Complete drug accountability.

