- Targeted physical examination (examination of heart, lungs, abdomen, lower extremities, skin (presence of rash) and lymph nodes);
- Weight (without shoes preferred);

- Specific Medical History: History of uveitis, psoriasis, inflammatory bowel disease and peripheral articular involvement as assessed by swollen joint count;
- BASMI (linear function) obtained by qualified blinded assessor: Lateral spinal flexion, tragus-to-wall distance, lumbar flexion (modified Schober), maximal intermalleolar distance and cervical rotation;
- Spinal mobility obtained by qualified blinded assessor: chest expansion;
- Assessment of swollen joints (44-joint count) by qualified blinded assessor;
- Assessment of enthesitis using the MASES Index by qualified blinded assessor;
- Complete drug accountability.

Procedures to be performed after dosing:

- Monitoring of adverse events and concomitant treatments. Record any modifications, deletions or additions;
- Contraception check: Confirm and document that proper contraception is being used;
- Risk factor check for VTE ([Section 7.1.14](#));
- Contact IWRS and dispense new supply of study medication to subject;
- Instruct subject not to take the in-clinic dose of investigational product the day of the next study visit but to bring the drug supply with them to the visit.

6.2.9. Week 40

There is a ± 7 day window for this visit.

- All PROs should be completed prior to any other study procedures. These include the following: ASAS/ASDAS_{CRP} Component: “Patient Global Assessment of Disease (NRS)”, “Patient Assessment of Spinal Pain” which includes Total Back Pain (NRS) and Nocturnal Spinal Pain (NRS), BASDAI (NRS), BASFI (NRS), and FACIT-F.

After the PROs are obtained, the following procedures should be completed prior to dosing:

- Verify morning dose of investigational product was not administered by subject. If the dose was administered, continue with visit but re-instruct subject on the requirement for in-clinic dosing;

Note: For subjects where the visit is conducted in the afternoon or evening, verify the afternoon or evening dose of investigational product was not administered by the

subject. Vital signs: Blood pressure (seated), pulse rate and temperature (via tympanic, oral or temporal, preferred);

- Laboratory testing: Hematology, Chemistry Panel, Urinalysis, Urine Pregnancy Test (for women of childbearing potential only), hsCRP;

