8.2.5. Serious Infections

A serious infection is any infection (viral, bacterial, and fungal) that requires hospitalization for treatment or requires parenteral antimicrobial therapy or meets other criteria that require it to be classified as a serious adverse event. A subject who experiences a serious infection should be discontinued from the investigational product and the serious adverse event should be listed as the reason for discontinuation in the CRF. Appropriate laboratory investigations, including but not limited to cultures should be performed to establish the etiology of any serious infection. All adverse events, including serious adverse events, should be reported as described in [Section 8](#) on Adverse Event Reporting.

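### At Weeks 4, 8, 12, 24, 32 and 40 the adverse-event and co-medication enquiry is listed after the in-clinic dose, so a reason to hold or stop may surface one tablet late

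*Protocol*

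**What the plan says.** Protocol 5.5 has the visit-day dose taken in the clinic. Sections 6.2.2 to 6.2.10 list the steps of each post-baseline visit.

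- **Weeks 4 and 32 (6.2.3, 6.2.8).** The heading "Procedures to be performed after dosing" stands over the AE and co-medication item.
- **Week 8 (6.2.4).** "Monitoring of adverse events and concomitant medications" falls under a shorter after-dosing heading.
- **Weeks 12, 24 and 40 (6.2.5, 6.2.7, 6.2.9).** "Monitoring of adverse events and concomitant treatments" falls under the same shorter heading.
- **Weeks 32 and 40.** The VTE risk-factor check is in the after-dosing block as well.
- **Week 16 (6.2.6).** The order is reversed: "Monitoring of adverse events and concomitant treatments. Record any modifications, deletions or additions" comes first, and "Administer in-clinic dose of investigational product from open-label study drug supply" follows.

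The enquiry is active: 8.1.2 has every subject questioned about AEs. What it finds can matter for dosing. Section 5.5 withholds product while suspected VTE is evaluated, and allows discretionary holds for non-serious infections and other medical conditions (double-blind period) or for infections, moderately severe AEs and other reasons (open-label period). Section 6.4.2 lists the permanent stops. On two of them the protocol says elsewhere: "Subjects who require rescue for more than 10 consecutive days will be discontinued from the investigational product" (5.8.3) and "A subject who experiences a serious infection should be discontinued from the investigational product" (8.2.5).

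**The concern.** A question whose answer can lead to withholding a dose does its work best before that dose. At six visits an explicit heading directs the site the other way. A subject who has told nobody about leg swelling, a hospital-treated infection or two weeks of rescue analgesia would be given a supervised tablet, then asked, and only then held or stopped under 5.5 or 6.4.2. No visible text in these sections requires the enquiry before the dose.

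The stake is a small matter of patient safety. The primary and secondary endpoints, the Type I error control and the power do not depend on it.

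**Working it through.** The plan gives no figure on this point, so the check is a reading of the visit lists and a count.

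**1. Position of the AE and co-medication item relative to the in-clinic dose** (Protocol 6.2.2 to 6.2.10)

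| Visit | Position | VTE risk-factor check |
|---|---|---|
| Week 2 | after, by list order only | not scheduled |
| Week 4 | after, explicit heading (dose step redacted) | not scheduled |
| Week 8 | after, explicit heading (dose step redacted) | not scheduled |
| Week 12 | after, explicit heading | not scheduled |
| Week 16 | before | not scheduled |
| Week 24 | after, explicit heading | not scheduled |
| Week 32 | after, explicit heading | after, explicit heading |
| Week 40 | after, explicit heading | after, explicit heading |
| Week 48 | after, by list order only | after, by list order only |

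Explicitly after: 6 of 9 visits. By list order only: 2 of 9. Before: 1 of 9.

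**2. What is listed before the dose.** At Weeks 12, 24, 32 and 40 nothing is redacted. Once the patient-reported outcomes are done, the block holds dose verification, vital signs, laboratory sampling (with cell-sorting blood at Week 32) and then the dose. It contains no AE or co-medication question. The targeted physical examination may be done before or after dosing.

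**3. Which stop rules the enquiry can reach.** Section 6.4.2 has 16 criteria:

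- 9 rest on two sequential laboratory values (neutrophils, lymphocytes, hemoglobin, platelets, three transaminase rules, creatinine, creatine kinase);
- 1 rests on a pregnancy test;
- 1 rests on interruption or compliance;
- 5 remain: serious infection, significant opportunistic infection, rescue beyond 10 consecutive days, other serious or severe AE, confirmed VTE.

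9 + 1 + 1 + 5 = 16. Five is an upper bound, because opportunistic infection and confirmed VTE need a diagnosis or evaluation that the question alone does not supply. That leaves 5 − 2 = 3 that a subject's answer could reveal directly. The holds in 5.5 come on top of these.

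**4. Exposure.** Scheduled tablets: 48 weeks × 7 days × 2 per day = 672. One tablet is 1/672 = 0.15%. A stop event ends dosing, so it normally accounts for one tablet per subject. Temporary holds can recur; the ceiling, a subject affected at all six visits, is 6/672 = 0.9%. Randomization is 1:1, so the tablet is placebo for about half of subjects at Weeks 4, 8 and 12. At Weeks 24, 32 and 40 it is tofacitinib 5 mg for everyone.

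**5. Number of subjects affected.** The documents give no rate for unreported events of this kind, so no count is estimated.

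**The case against.** The strongest reply is that the hold and stop rules do not hang on a visit item. They apply whenever the site learns of an event, AEs are collected from consent onward (8.1.4), and subjects are told: "Contact the study site investigator if there are any changes or additions to concomitant medications" (4.4). Vital signs precede the dose, and the targeted examination, which covers heart, lungs and lower-limb edema, may precede it too. The affected subject has usually been dosing at home already, and the hold or stop follows within the same visit.

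All of this stands, and it makes the enquiry a backstop. It does not remove the point. The reporting instruction in 4.4 covers co-medication and not VTE symptoms, the timing of the examination is optional, and vital signs do not reveal prolonged rescue use. The active question exists for what was not volunteered.

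Three stronger readings are tempting, and the documents do not support them:

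- *That sites are told to dose subjects with a known reason to stop.* They are not. The order matters only for what the site has not yet heard.
- *That the late VTE risk-factor check itself breaches a hold rule.* Under 7.1.14 a risk factor alone requires no hold; the subject may continue after a benefit-risk assessment. The hold in 5.5 is for suspected VTE.
- *That Week 16 shows the authors adopting a safer order.* The protocol's document history explains that sequence as collecting data before open-label dosing. It shows that the order is workable and says nothing about safety intent.

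**Conclusion.** The point holds as a minor ordering issue. At six of nine post-baseline dosing visits the protocol explicitly lists the AE and co-medication enquiry after the supervised dose, and at two of the six the VTE risk-factor check as well. For Weeks 4 and 8 this rests on the visible heading, since the dose step is redacted. Weeks 2 and 48 are left out of the claim because there the order follows from list position alone.

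The size is one tablet per affected visit, 0.15% of the scheduled total. The conclusion assumes that sites follow the listed order and that the event had not already reached them by another route.

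**What to change.** In Protocol 6.2.3 to 6.2.5 and 6.2.7 to 6.2.9, move AE and co-medication monitoring, and the VTE risk-factor check where present, to after the patient-reported outcomes and before the dose. For AE and co-medication this is the list order Week 16 already uses. At Weeks 4 and 8 the sponsor, who has the unredacted text, can place the items relative to the hidden dose step. Weeks 2 and 48 could be aligned in the same edit for consistency.

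The patient-reported outcomes stay first, and no procedure, visit, dose, hold or stop rule changes. There are two costs. One is a minor change in site workflow, to be carried in a protocol amendment with the approval that 12.1 requires. The other is loss of the scheduled question after the supervised dose; events arising then would still be captured by observation, by spontaneous report (8.1.2) and at the next visit.

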6.3. Follow-up Visit

The Follow-up visit is required of all subjects who complete the study or are withdrawn from the investigational product after the Week 40 visit. These subjects must have a Follow-up visit within 28 days (± 7 days) of the Week 48 visit. Subjects who are withdrawn from the investigational product prior to the Week 40 visit are not required to have a follow-up visit after they complete the study at the Week 48 visit. There is a ± 7 day window for this visit.

All subjects who complete or discontinue early from the investigational product after Week 40 must have a Follow-up visit within 28 days (± 7 days) of the Week 48 visit.

Subjects are required to fast for at least 9 hours prior to the visit; however, blood collection for laboratory testing may be taken up to 48 hours prior to or following this visit as necessary to ensure the samples are collected in a fasting state.

The following procedures will be performed:

- Targeted physical examination (examination of heart, lungs, abdomen, lower extremities, skin (presence of rash) and lymph nodes);
- Weight (without shoes preferred);
- Specific Medical History: History of uveitis, psoriasis, inflammatory bowel disease and peripheral articular involvement as assessed by swollen joint count;
- Vital Signs and temperature: Blood pressure (seated), pulse rate and temperature (via tympanic, oral or temporal, preferred);
- Laboratory testing: Central laboratory tests include: Hematology, Urinalysis, Chemistry Panel, Lipid Profile (fasting), Urine Pregnancy Test (for women of childbearing potential only), hsCRP;
- Adverse event reporting and concomitant treatment use;

- Risk factor check for VTE ([Section 7.1.14](#));
- Contraception check: Confirm and document that proper contraception is being used.

If abnormalities in hematology or chemistry results or adverse events with a causal relationship to the study medication are still observed/ongoing at the follow-up visit, the subject must continue to be followed until the laboratory abnormality or adverse event stabilizes or returns to baseline levels as approved by the Sponsor.

